2.1.1 Primary Objectives

The primary objectives of this study are:

- To define the safety and tolerability of pracinostat plus azacitidine in high/very high risk MDS
- To define the rate of overall response rate (ORR), defined as complete remission (CR) and partial remission (PR), of pracinostat plus azacitidine in high/very high risk MDS

2.1.2 Secondary Objectives

The secondary objectives of this study are:

- Complete response (CR) rate
- Overall hematologic improvement (HI) response rate
- Clinical benefit rate, defined as rate of CR + PR + HI + Marrow CR
- Rate of cytogenetic complete response/remission
- Duration of response (DoR)
- Rate of leukemic transformation
- Duration of event-free survival (EFS)
- Duration of progression-free survival (PFS)
- Duration of overall survival (OS)

2.2 Treatment Groups

All Stage 1 and Stage 1b subjects will receive pracinostat and azacitidine. Treatment will be open-label.

2.3 Study Endpoints and Evaluations

2.3.1 Primary Endpoints

The primary efficacy endpoint is overall response rate (ORR) – defined as the proportion of subjects with confirmed complete response (CR) or partial response (PR) according to IWG criteria [1]. The ORRs will be assessed for both stages.

The primary safety endpoint is subject incidence of treatment emergent adverse event (TEAEs).

2.3.2 Secondary Endpoints

The secondary efficacy endpoints are:

- Complete remission (CR) rate: proportion of subjects with confirmed CR (i.e. 2 CRs at least 28 days apart) per IWG criteria. CR is defined as:
 - Bone marrow: $\leq 5\%$ myeloblasts with normal maturation of all cell lines; persistent dysplasia will be noted.
 - Peripheral blood (in the absence of transfusions)
 - Hemoglobin ≥ 11 g/dL
 - Platelets $\geq 100 \times 10^9/L$
 - Neutrophils $\geq 1.0 \times 10^9/L$
 - Blasts 0%
- Overall hematologic improvement (HI) rate: proportion of subjects who demonstrate major hematologic improvement per IWG criteria, for at least one criterion. Only subjects with pre-treatment abnormal values will be considered for this evaluation at 8 weeks.
- Clinical benefit rate (CBR): proportion of subjects with confirmed CR, PR, Marrow CR, or HI. All subjects who achieve hematologic CR, PR, marrow CR (with or without HI), or HI without marrow CR per IWG will be considered responders. PR is defined as all of the CR criteria if abnormal before treatment except bone marrow blasts, which can be decreased by $\geq 50\%$ over pretreatment but still $> 5\%$, and cellularity and morphology are not relevant. Marrow CR is defined, only in patients with MDS with excess blasts, as:
 - Bone marrow: $\leq 5\%$ myeloblasts and decrease by $\geq 50\%$ over pretreatment
 - Peripheral blood: if HI responses, they will be noted in addition to marrow CR
- Relapse: after CR or PR, at least one of:
 - Return to pretreatment bone marrow blast percentage

- Decrement of $\geq 50\%$ from maximum remission/response levels in granulocytes or platelets
 - Reduction in hemoglobin concentration by ≥ 1.5 g/dL or transfusion dependence
- Cytogenetic complete response/remission rate: proportion of subjects with disappearance of the chromosomal abnormality without appearance of new ones, by cytogenetic assessment in the subset of subjects with abnormal cytogenetics at baseline.
- Duration of response (DOR) will be derived in 2 ways: for subjects who achieve CR or PR (primary), and for subjects who achieve CR, PR, marrow CR or HI: time from initial determination of response to time of disease progression or death on study, whichever occurs first. For subjects who are alive and have not experienced disease progression on study (prior to receiving subsequent/new treatment or stem cell transplant), duration of response will be censored at the day of last disease assessment.
- Leukemic transformation rate: leukemic transformation at landmark time points of 6, 12, 18, and 24 months.
- Event-free survival (EFS), defined as the time from the first day of study drug administration (Day 1) to disease progression, relapse or death from any cause. Subjects who are alive and free from disease progression will be censored at the date of last disease assessment .
- Progression-free survival (PFS): time from the first day of study drug administration (day 1) to progression per IWG criteria, or death on study. Subjects who are alive and free from disease progression will be censored at the date of last disease assessment.
- Overall survival (OS): time from the first day of study drug administration (day 1) to death from any cause on study. Subjects who are alive will be censored at the date of last visit or contact with the investigator.
- Time to Stem Cell Transplant (SCT): time from the first day of study drug administration (day 1) to SCT, for subjects with SCT. If no SCT date can be confirmed, SCT date will be imputed as study drug discontinuation day.

For each of DOR, EFS, PFS and OS, in the sensitivity analyses, subjects with no events who stopped treatment and received SCT will be censored at the SCT day (either confirmed SCT day, or study drug treatment discontinuation day, if no SCT date can be confirmed) even if there were events which occurred after the SCT date.

- For both stages, the rate of treatment discontinuation in the first 3 cycles of therapy due to possibly safety-related reasons will be used as a secondary endpoint to evaluate the safety and tolerability. Progressive disease and transplant are reasons to discontinuation related to efficacy, therefore these events will be excluded from the analysis. All the other reasons for treatment discontinuation will be considered as possibly safety-related, therefore will be included in the analysis as events.

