A BMBx and aspirate to assess cellularity, blast percentage, morphology (dysplasia), and cytogenetics (if abnormal at baseline), as well as a CBC with differential will be required at the end of Cycles 2 and 6, with evidence of disease progression, with evidence of hematologic CR which may occur after Cycle 6, and prior to transplant if the subject becomes a candidate for transplant. Once a marrow CR is documented, there is no need to repeat a BMBx unless clinically indicated.

Ideally, transplant will be after the conclusion of ≥ 4 cycles of therapy. The following assessments are to be performed, and the Medical Monitor is to be advised of the results prior to discontinuing treatment for transplant:

- Bone marrow biopsy and aspiration (classic cytogenetics, fluorescence in-situ hybridization [FISH], and molecular studies, if done at baseline).*
- CBC with differential and blasts.

* FISH and molecular studies are not required by protocol, but results should be collected in the electronic data capture (EDC) system if performed as per local practice.

Transfusions in the 8 weeks prior to starting study drugs and while on study and hematopoietic growth factor use will also be captured to assess efficacy.

Local (i.e., Investigator) assessments of response will be utilized for the primary efficacy analyses, employing the IWG standardized response criteria for evaluating clinically significant responses in MDS ([Cheson 2006](#)). These criteria measure alterations in the natural history of disease, hematologic improvement, cytogenetic response, and improvement in health-related quality of life. Diagnosis of MDS according to the WHO classifications are presented in [Appendix B](#).

The IWG Response Criteria for MDS are presented in [Appendix D](#). The response categories are as follows:

- CR
- PR
- Marrow CR
- HI
- Stable Disease
- Failure
- Relapse after CR or PR
- Cytogenetic Response
- Disease Progression
- Survival

A CBC with differential will be required for confirmation of CR or PR 8 weeks following the initial report of response.

Modified IWG response criteria are presented in [Appendix D](#).

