7.1.4 Precautions and Risks Associated with the Study Drug

Precautions and associated risks with pracinostat	
Hematologic	Treatment with pracinostat has been associated with cytopenias including anemia, thrombocytopenia, and neutropenia. The incidence of cytopenias may increase with increasing doses of pracinostat. Subjects participating in clinical studies of pracinostat should be monitored closely for adverse hematologic affects. The effect of dose reduction on the amelioration of cytopenias has not been established, however prudent clinical management, including supportive care (appropriate use of transfusions and/or hematopoietic growth factors) and dose modification or discontinuation should be followed (see Section 6.5).
Gastrointestinal	Gastrointestinal disturbances (including nausea, vomiting, and diarrhea) have been reported in subjects treated with pracinostat. Standard antiemetic and antidiarrheal medications and appropriate supportive care should be used per normal clinical practice in subjects participating in clinical studies of pracinostat. Preexisting nausea, vomiting, and diarrhea should be adequately controlled before beginning therapy.
QTc Prolongation/Cardiac	Asymptomatic QTc interval prolongation has been observed during clinical studies of pracinostat. Subjects with a CTCAE Grade 2 prolonged QTc interval during screening will not be permitted to participate in clinical studies of pracinostat. Hypokalemia or hypomagnesemia should be corrected prior to pracinostat administration and consideration should be given to monitoring potassium and magnesium in symptomatic subjects (e.g., subjects with nausea, vomiting, diarrhea, fluid imbalance, or cardiac symptoms). See the Investigator's Brochure for additional information on QTc prolongation. Concomitant medications with a known risk of prolonging the QT interval and/or causing Torsades de Pointes are prohibited. In addition, caution should be taken when using concomitant medications with a possible or conditional risk of prolonging the QT interval and/or causing Torsades de Pointes; medications with a possible or conditional risk may be used at the discretion of the Investigator (Appendix H).

Precautions and associated risks with pracinostat	

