8.1 Permitted Concomitant Medications

Premedication with antiemetics is allowed according to standard practice guidelines and/or local standards of care.

Prophylaxis with quinolone antibiotics is permitted per local standards of care.

Caution should be taken in concomitant administration of the following:

- Fibrinolysis inhibitors
- Anticoagulant and antiplatelet drugs

Other medications considered necessary for subject safety and well-being may be given at the discretion of the Investigator with the exception of those listed in Section 8.2.

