8.2 Prohibited Concomitant Medications

The following treatments are prohibited while in this study:

- No other investigational therapy should be given to subjects.
- No anticancer agents should be administered to subjects. If such agents are required, the subject must first be withdrawn from the study.
- HDAC inhibitors (Zolinza [vorinostat], Istodax [romidepsin/depsipeptide]) or valproic acid (which has significant action as a HDAC inhibitor).

- Medications with a known risk of prolonging the QT interval and/or causing Torsades de Pointes.
- Herbal preparations (e.g., St John's wort) are not allowed throughout the study. Subjects must discontinue herbal medications at least 7 days prior to the first dose of study treatment.
- Patients should avoid grapefruits, grapefruit juice, and Seville oranges during the study since they are known to be inhibitors of CYP3A4.
- Smoking or vaporizing of tobacco or cannabis-related products is prohibited. These products must be discontinued at least 8 days prior to the first dose of study treatment. [Note: Nicotine gum or patches are allowed, as is chewing tobacco].
- Prophylactic G-CSF may be used only in subjects with a treatment-emergent AE of febrile neutropenia while on study, or in subjects with persistent (> 5 days) Grade 4 neutropenia who are at high risk for development of febrile neutropenia.

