9.1 Primary Endpoint Analysis

Overall response rate

The primary efficacy endpoint is overall response rate (ORR) defined as complete remission (CR) or partial remission (PR) per IWG criteria. The ORR and associated 95% confidence interval will be calculated using an exact binomial distribution approach for each of the ITT, EE and PP populations. For the PP population, the response rate will also be summarized by treatment schedule. In addition, a waterfall plot of the percentage change in blasts will be provided, and a forest plot of the ORR and corresponding 95% confidence intervals will be provided for each of the risk factors detailed in section 6.3.

If the ORR is shown to differ between the two treatment schedules, additional tables split by treatment schedule may be provided,

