9.2.1.2 Overall hematologic improvement (HI) response rate

Overall hematologic improvement (HI) response rate will be defined as the proportion of subjects who demonstrate confirmed major hematologic improvement as defined by IWG criteria (i.e. 2 HIs at least 8 weeks apart), for at least one criterion. Only subjects with pre-treatment abnormal values will be considered for this endpoint. The response rate and associated 95% confidence interval will be calculated using an exact binomial distribution approach for the ITT, EE and PP populations.

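### The CR and PR rules exclude only transfusion-supported counts and the HI rule excludes none, so counts held up by sustained growth factor use can be scored as response, mainly for HI and clinical benefit

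*SAP*

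**What the plan says.** **Response rules.** SAP Section 2.3.2 introduces the CR thresholds (hemoglobin at least 11 g/dL, platelets at least 100 × 10⁹/L, neutrophils at least 1.0 × 10⁹/L, no blasts) with "Peripheral blood (in the absence of transfusions". It adds that "PR is defined as all of the CR criteria if abnormal before treatment except bone marrow blasts", so PR uses the same blood criteria. SAP Section 9.1 states: "The primary efficacy endpoint is overall response rate (ORR) defined as complete remission (CR) or partial remission (PR) per IWG criteria". For HI, SAP Section 9.2.1.2 counts "the proportion of subjects who demonstrate confirmed major hematologic improvement as defined by IWG criteria (i.e. 2 HIs at least 8 weeks apart". It requires abnormal pretreatment values and sets no condition on support during treatment.

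**Protocol Appendix D.** The CR row has no support condition. The HI table asks that pretreatment counts be free of transfusion influence and limits which red cell transfusions count toward the transfusion route of HI-E. It does not mention growth factors.

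**Growth factor use on study.** For cytopenias, protocol Section 7.1.4 names "supportive care (appropriate use of transfusions and/or hematopoietic growth factors". Section 8.1 says "Other medications considered necessary for subject safety and well-being may be given at the discretion of the Investigator", apart from what Section 8.2 lists. Section 8.2 says "Prophylactic G-CSF may be used only in subjects with a treatment-emergent AE of febrile neutropenia while on study", or in high-risk subjects with Grade 4 neutropenia lasting more than 5 days. It does not list erythropoietic agents (ESAs) or thrombopoietin receptor agonists.

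**Entry.** Exclusion criterion 2 sets a growth factor washout of 7 days, or 14 days for Aranesp.

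**Data.** Protocol Section 5.2.4 states that transfusions before treatment and "while on study and hematopoietic growth factor use will also be captured to assess efficacy".

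**The concern.** The SAP recognizes that a supported blood count is not evidence of response, but it acts on this for transfusions only. The protocol says growth factor data serve the efficacy assessment, yet no derivation, window or sensitivity analysis in either document uses them. A programmer or site applying the written rules would accept a hemoglobin, platelet or neutrophil value obtained under growth factor support.

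Response is assessed locally at approximately 25 sites, so without a rule the handling may also vary between sites. The trial has a single arm, so no concurrent control shares any resulting shift. The results concerned are HI, clinical benefit (which counts HI), CR and, by a narrower route, the primary ORR.

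**Working it through.** **1. Which rule stops which supported count?**

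| Endpoint | Transfusion condition on treatment | Growth factor condition | Confirmation | Also needs marrow criterion |
|---|---|---|---|---|
| CR | yes (SAP 2.3.2) | none | 2 CRs at least 28 days apart; CBC at 8 weeks (protocol 5.2.4) | yes |
| PR | through CR | none | 2 PRs, or a PR then a CR, at least 28 days apart; CBC at 8 weeks | yes |
| HI by counts | none | none | 2 HIs at least 8 weeks apart | no |

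- The confirmation rules remove brief effects. A neutrophil count that rises after a short G-CSF course and then falls does not qualify.
- They do not remove support that continues across the confirmation interval.
- HI is the most exposed: one lineage suffices and no marrow criterion applies.

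**2. How can ORR be reached?** Growth factors alone cannot produce CR or PR. Two routes remain.

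- *Marrow CR to CR.* Marrow CR lies outside ORR. SAP Section 9.2.1.1 lets the blood criteria be met over the next 6 cycles after the marrow criterion, with confirmation on blood. Protocol Section 5.2.4 asks for no routine repeat biopsy once marrow CR is documented. Blood counts then decide the category.
- *Marrow blast reduction to PR.* A marrow blast reduction of at least 50%, with blasts still above 5%, becomes PR when the blood criteria are met.

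**3. Reproducing the plan's figures.** Inputs are N = 60, an observed ORR of 40% and a 25% reference (SAP 4.2), with exact binomial intervals (SAP 9.1). The lower limit for x responders of n is the 0.025 quantile of Beta(x, n − x + 1).

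- 24/60: Beta(24, 37) gives 27.56%; the plan states 27.6%.
- 21/60: 23.13%; the plan's table gives 23.1%.
- 18/40: 29.26%; SAP 4.1 states 29.3%.

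**4. Sensitivity.** The documents give no rate of growth factor use among responders. Let k, an assumed number, be the CR/PR responders who would not qualify without support.

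| k | Responders of 60 | ORR | Exact lower limit |
|---|---|---|---|
| 0 | 24 | 40.0% | 27.6% |
| 1 | 23 | 38.3% | 26.1% |
| 2 | 22 | 36.7% | 24.6% |
| 3 | 21 | 35.0% | 23.1% |
| 4 | 20 | 33.3% | 21.7% |

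Each subject is worth 1/60 = 1.7 percentage points. The smallest count with a lower limit above 25% is 23, so from 24 the second reclassified subject crosses the reference. In the SAP's Stage 1 example, removing two from 18/40 leaves 16/40 = 40.0%, with a lower limit of 24.9%.

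No comparable calculation is possible for HI or clinical benefit, because the plan assumes no rate for either.

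**The case against.** The strongest reply has five parts.

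- **The cited criteria.** Response is defined by citation of published IWG criteria. Their full text is not part of these documents, and Appendix D notes that deletions are not shown. That source may deal with growth factors. This stands as a limit: the gap shown is in the text that the protocol and SAP supply.
- **Durability and marrow requirements.** A reader might infer that any count taken soon after G-CSF scores as response. The documents do not support that, given the 28-day and 8-week rules and, for CR and PR, the marrow criteria. G-CSF is also restricted to stated circumstances. ESA and thrombopoietin agonist use is inferred from a generic reference to growth factors, the discretion clause and the absence of a prohibition; no clause names either as on-study therapy. This stands, and it makes the ORR route narrow.
- **Direction.** A reader might infer that baseline counts are always free of growth factors, so that bias can only raise response. That is not assured. The two screening CBCs may be up to 1 month old, and Appendix D averages at least two pretreatment values. One may precede the washout, which would raise the comparison value and make HI harder to reach.
- **Benchmark.** How the azacitidine studies behind the 25% figure handled growth factors is not stated, so a stricter rule here might reduce comparability. This stands.
- **Investigator assessment.** The primary analysis uses local response assessments, and a hard exclusion could override them. This bears on the form of the fix. It does not supply the missing rule.

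**Conclusion.** The gap is real. The SAP conditions CR, and so PR, on absence of transfusion support only, and count-based HI on no on-treatment support condition. Growth factors may be used, and their use is collected for efficacy. Applied as written, the rules can score sustained growth factor support as response.

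The effect falls mainly on HI and clinical benefit. For ORR it is limited to subjects whose marrow already meets the relevant criterion and whose category turns on blood counts. The size is unknown. The fall in the lower limit from 27.6% to 24.6% rests on an assumed 2 supported responders out of 24. It shows how close the plan's favorable result lies to its reference, and it is not an estimate of bias. A reader might infer that ORR is already inflated by some such number; nothing in the documents shows that. The analyses are descriptive, so no formal test is affected. The point warrants a change to the SAP before analysis.

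**What to change.** In SAP Sections 2.3.2, 9.2.1.1 and 9.2.1.2:

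1. For CR and PR, require qualifying counts to be free of both transfusion support and hematopoietic growth factor support for the lineage concerned.
2. Apply the same condition to HI-E by hemoglobin, HI-P and HI-N.
3. Define support by a prespecified window for each agent. The protocol's entry washout (7 days, or 14 days for Aranesp) is one available choice. The documents do not establish that it suits this purpose, so the SAP should justify whatever is chosen.

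If the sponsor prefers to leave investigator-assessed response as the primary rule, the minimum is a prespecified sensitivity analysis of ORR, CR, HI and clinical benefit that treats counts inside the window as non-qualifying. Under either option, report the number of responders affected.

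**Cost.** One additional derivation from transfusion, growth factor and concomitant medication data already collected. Response rates may be slightly lower, some results may depart from the investigator's assessment, and scoring may differ from that behind the historical benchmark. Treatment and supportive care do not change.
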